Document: Statistical Analysis Plan

Official Study Title: Digital Community to Improve Health in Rural Areas

NCT Number: NCT05363865

Document Date: 03/04/2025

Statistical Analysis Plan – AG C-RCT

The statistical analyses will examine the intervention effect (i.e., experimental versus control) on the primary, secondary, and tertiary outcomes, with the covariate of individuals' drug use status (i.e., PWUD versus PWNUD) (see Table 1). The primary analyses will be conducted using the intention-to-treat (ITT) method. That is, all participants who completed the baseline measure will be included in the analyses by replacing missing data by carrying forward the last observation. We will perform multi-level modeling with clustered cohorts and report the intra-class correlations (ICC) of the cohort (i.e., group). In these models, we will specify 16 models with four sets of random effects models (i.e., random intercept only, random slope only, random intercepts and slopes without their correlations, and random intercepts and slopes with their correlations) and select the best one based on model-fit indices (i.e., AIC, BIC, and the likelihood ratio test).

The primary outcome is a composite score summing six yes/no behaviors promoted in the intervention: (a) HIV testing, (b) HCV testing, (c) HIV prevention, (d) requesting Naloxone before the assessment time point (i.e., the requests made at the immediate follow-up are counted for the 3-month follow-up), (e) carrying Naloxone, and (f) making or rebuilding at least one social connection. The assessment of HIV prevention depends on each participant's sexual risk and drug injection risk and includes PrEP use, use of condoms during sex, use of syringe service programs, and disinfecting injection equipment. Specifically, individuals engaging in sexual behaviors receive a score of 1 if they report using condoms during sexual encounters or using PrEP. Likewise, individuals at risk of drug injection receive a score of 1 if they report using PrEP, using syringe service programs, or disinfecting their injection equipment. For participants

who neither engage in sexual behaviors nor are at risk of drug injection, an HIV prevention score of 1 is recorded. The primary outcome is treated as a continuous variable, ranging from 0 to 6.

For the secondary and tertiary outcomes (see Table 1), we will specify a binomial family for the analysis of binary data. For outcomes about change, such as substance use frequency, baseline responses will be subtracted from those obtained at the follow-up assessments (i.e., T1 – T0). We will impose no alpha correction/adjustment for multiple outcome comparisons because we have no conjunction hypotheses and these outcomes are not the primary outcome.

The design of the study allows for the assessment of the total effect of the Zoom sessions, GROV app, and HIV/HCV testing and Narcan kit availability. Therefore, that test is possible only for the immediate follow-up and will be conducted in an initial outcome paper that examines the efficacy of this multi-level program.

The 3-month and 6-month follow-ups provide an idea of the impact of the intervention when all participants have the option of receiving HIV/HCV testing and Narcan kits and also permit an examination of the durability of the effects. Therefore, these outcomes will be reported in a second paper.

We will carry out the following sensitivity analyses: (a) modified ITT analyses (i.e., including only those experimental participants who attended at least one session); (b) per-protocol analyses (i.e., including only data from participants who completed all three Zoom sessions originally allocated); and (c) analyses including relevant baseline measures, GROV activities, intervention process evaluation, fidelity assessment, and HIV/HCV testing and Narcan kit shipment schedules as covariates to assess the robustness of the results. The sensitivity analyses described here are not exhaustive, and new analyses can be added based on the research

team's decision (e.g., replacing the request data with the delivery/shipment data in the composite score).

We will also carry out process analyses by examining the content of the sessions with ChatGPT 4.0 (or later versions) and testing if these variables, as well as the number of sessions attended and GROV use, correlate with the study outcomes in the intervention group.

Table 1.
C-RCT Outcomes

Primary Outcome	Secondary Outcomes	Tertiary Outcomes
Sum of Yes to (a) self-testing for HIV, (b) self-testing for HCV, (c) HIV prevention, (d) requesting Naloxone, (e) carrying Naloxone, and (f) making at least one social connection (new or reestablished).	HIV and HCV testing	Seeking substance use or mental health treatment or recovery services (i.e., attending a 12-step group or another abstinence-based program, attending a substance use treatment program that uses medications, and/or attending a faith-based substance use group and being referred to healthcare and mental health/substance use recovery)
	HIV prevention behaviors (i.e., PrEP use, use of condoms during sex, use of syringe service programs, and disinfecting injection equipment)	Interacting positively with people who use substances during and outside the sessions and drug stigma
	Requesting Naloxone (Narcan)	Substance use without a prescription or more than prescribed (with baseline level at 3 and 6 months)
	Carrying Naloxone (Narcan)	Injection substance use (with baseline level at 3 and 6 months)
	Making social connections (new or reestablished)	Seeking treatment for HIV and HCV if participant is seropositive

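### Sensitivity analysis (c) lists baseline covariates together with parts of the intervention, so it cannot test robustness of the total effect; the main models also leave out the baseline outcome, which costs precision

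*SAP*

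**What the plan says.** The opening paragraph of the SAP sets out the main analysis of "the intervention effect (i.e., experimental versus control) on the primary, secondary, and tertiary outcomes, with the covariate of" drug use status. It names no other covariate. The same paragraph states that "all participants who completed the baseline measure will be included in the analyses", with missing values filled by the last observation. The primary composite is a 0 to 6 score and is not defined as a change.

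The paragraph on sensitivity analyses plans, as item (c), "analyses including relevant baseline measures, GROV activities, intervention process evaluation, fidelity assessment, and HIV/HCV testing and Narcan kit shipment schedules as covariates", and presents this as a check of robustness. It adds that further analyses may be run, for example "replacing the request data with the delivery/shipment data in the composite score".

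The paragraph on the immediate follow-up says that the design assesses "the total effect of the Zoom sessions, GROV app, and HIV/HCV testing and Narcan kit availability", and that this test is possible only at that time point. The later follow-ups describe the period "when all participants have the option of receiving HIV/HCV testing and Narcan kits".

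For outcomes about change, "baseline responses will be subtracted from those obtained at the follow-up assessments". Table 1 mentions baseline for two tertiary outcomes only, injection substance use and "Substance use without a prescription or more than prescribed (with baseline level at 3 and 6 months").

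**The concern.** A robustness analysis should estimate the same quantity as the main analysis under different assumptions. Item (c) does not do so when it conditions on GROV activity or kit shipment. These arise after randomisation and belong to what is being tested. The SAP even offers delivery and shipment data as a component of the composite, so shipment could be an outcome in one sensitivity analysis and a covariate in another. A reader who sees a smaller effect under (c) could conclude that the main result is fragile, when the model has only removed part of the intervention. If all the listed variables enter one model, the informative result, namely what baseline adjustment alone does, cannot be read from it.

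The second matter is smaller. Everyone in the ITT population has completed the baseline measure, and carrying an observation forward for someone with no follow-up presupposes baseline values for at least some of the outcome. The main models for the primary and secondary outcomes nevertheless do not name that value as a covariate.

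**Working it through.** The SAP gives no sample size, correlation, ICC or cohort size, so there is no stated figure to reproduce. All inputs below are assumptions.

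**1. Conditioning on a part of the intervention.** Take 1:1 arms, individual-level data, a variable M that is 0 in all controls and 1 in a share u of experimental participants, and no common causes of M and the outcome.

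- Estimate with M held fixed = total effect × (1 − share running through M). With a total of 0.50 SD: 0.50 × 0.75 = 0.375 and 0.50 × 0.50 = 0.25. Simulation (400 participants, 4,000 runs) gave 0.37 to 0.38 and 0.25. Adjusting for baseline only left the estimate at 0.50.
- The squared correlation of arm and M is u/(2 − u), so the variance of the arm effect is multiplied by (2 − u)/(2 − 2u). For u = 0.5 / 0.7 / 0.9 this is 1.5 / 2.17 / 5.5, and the SE is multiplied by 1.22 / 1.47 / 2.35.

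So the estimate moves and becomes less precise for reasons unrelated to robustness.

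**2. Baseline as a covariate in the main model.** The planned model already contains drug use status, so the relevant ρ is the partial correlation of baseline and follow-up given that status. The variance ratio is 1 − ρ², and the fall in SE is 1 − √(1 − ρ²).

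| Partial ρ | Variance ratio | Fall in SE |
|---|---|---|
| 0.1 | 0.99 | 0.5% |
| 0.2 | 0.96 | 2% |
| 0.3 | 0.91 | 5% |
| 0.5 | 0.75 | 13% |

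Some components, such as requesting Naloxone, may have little or no baseline variation. If k of 6 equal-variance, mutually uncorrelated components vary at baseline, each with same-component correlation r, then ρ = r√(k/6). For k = 3 and r = 0.3 / 0.5, ρ = 0.21 / 0.35 and the SE falls by 2.3% / 6.5%.

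**3. Clustering.** Assume that cohorts of m = 16 are randomised, the ICC is the same at both times, the adjustment slope equals the within-cohort ρ, and cohort effects at baseline and follow-up correlate at c. The adjusted to unadjusted variance ratio is then

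[ICC(1 − 2cρ + ρ²) + (1 − ICC)(1 − ρ²)/m] / [ICC + (1 − ICC)/m].

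- ICC 0.05, ρ = 0.3: denominator 0.05 + 0.95/16 = 0.1094.
  - c = 1 (identical cohort effects): (0.0245 + 0.0540)/0.1094 = 0.72.
  - c = ρ: 0.91.
  - c = 0 (unrelated): (0.0545 + 0.0540)/0.1094 = 0.99.
- ICC 0.10, c = 0: denominator 0.10 + 0.90/16 = 0.1563.
  - ρ = 0.3: (0.1090 + 0.0512)/0.1563 = 1.03, a small loss.
  - ρ = 0.5: (0.1250 + 0.0422)/0.1563 = 1.07.
  - Simulation with 10 to 30 cohorts gave 1.02 to 1.03 and 1.06 to 1.09.

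**4. Raw change against adjustment.** For a continuous outcome with equal variances, raw change has variance 2(1 − ρ) and the adjusted analysis 1 − ρ², both relative to follow-up alone. Their ratio is 2/(1 + ρ): 1.54 at ρ = 0.3, 1.33 at 0.5 and 1.18 at 0.7. It is never below 1. Against follow-up alone, raw change is worse below ρ = 0.5 (1.40 at 0.3) and better above it (0.60 at 0.7).

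**The case against.** Several points on the other side are fair.

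- A randomised ITT comparison with one covariate is valid. A reader might infer that omitting baseline biases the main estimate. It does not, and the plausible gain may be a few per cent of the SE.
- A reader might infer that (c) is one model holding every listed variable. The SAP speaks of analyses in the plural and does not settle it. Separate models would let the baseline-only result be seen. They would still label app-adjusted and shipment-adjusted results as robustness checks, so that part of the point does not depend on the reading.
- Item (c) is a sensitivity analysis and cannot alter the primary estimate. The harm is to interpretation.
- The SE factors assume that M is 0 in all controls. That may fit GROV activity, although the SAP does not describe the control condition. It does not fit shipment at 3 and 6 months, when everyone has the kit option. A shipment schedule is also not the same as kit availability.
- Baseline might already be used. Random slopes need a slope variable, and a repeated-measures model with T0 as a response is possible. The SAP names neither a time term nor T0 as a response, so this cannot be counted as pre-specified, but it does condition the fix.
- The only change outcome given as an example, substance use frequency, is not primary or secondary. The Table 1 note may already mean baseline adjustment for the two tertiary outcomes.

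**Conclusion.** The point holds, with (c) as the more important part. Whichever way (c) is modelled, an analysis that fixes GROV activity or kit shipment does not estimate the total effect that the SAP defines, and attenuation there says nothing about robustness. How large the attenuation would be cannot be known from the SAP; 0.50 falling to 0.375 or 0.25 illustrates assumed shares of 25% and 50%.

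The missing baseline covariate is an efficiency matter. At the individual level the SE falls by about 0.5% to 13% for partial correlations of 0.1 to 0.5. With clustering, the result ranges from a larger gain, if cohort effects persist, to a variance loss of 2% to 9% if they are unrelated over time and the ICC is 0.10. Raw change is at best equal to baseline adjustment under the stated conditions. The documents do not support calling the main analysis invalid, or saying that baseline is certainly unused.

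**What to change.** 1. Split (c). In (c1), adjust for baseline covariates only, named in advance and including the baseline value of the outcome. In (c2), examine GROV activities, process evaluation, fidelity and shipment variables. Place (c2) with the process analyses, which already relate GROV use and session attendance to outcomes in the intervention group, and do not call it a robustness check of the total effect.
2. Add the individual baseline composite as a fixed covariate in the primary model, listing which components were measured at baseline. Add the matching baseline item in secondary models where it was collected. If T0 is already a response in the multilevel model, say so instead.
3. For change outcomes, use baseline as a covariate in place of the raw difference, and state what the Table 1 note on baseline level means.

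The cost is SAP wording and one or two degrees of freedom per linear model, with the possible small precision loss shown above. No new data are needed where the baseline item exists, and the ITT rule already requires a completed baseline. Adding the cohort baseline mean is not proposed: with 10 cohorts and ρ = 0.3 it raised the variance by 6% to 15% in simulation.

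### Last observation carried forward is the only missing-data rule for the primary analysis, so dropout distorts the estimated effect and no listed sensitivity analysis replaces the rule

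*SAP*

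**What the plan says.** The opening paragraph of the SAP sets the primary analysis as intention-to-treat: everyone with a baseline measure is to be "included in the analyses by replacing missing data by carrying forward the last observation". The filled-in data then enter a multi-level model clustered by cohort. The outcome is a sum of six yes/no behaviours: "The primary outcome is treated as a continuous variable, ranging from 0 to 6".

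On the total effect of the programme, the SAP states that "that test is possible only for the immediate follow-up and will be conducted in an initial outcome paper". The later visits serve a second paper on durability: "The 3-month and 6-month follow-ups provide an idea of the impact of the intervention when all participants have the option" of tests and kits.

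Three sensitivity analyses are listed: (a) modified ITT, (b) per-protocol and (c) added covariates. The first two change the population and the third changes the covariates. The SAP adds: "The sensitivity analyses described here are not exhaustive, and new analyses can be added based on the research" team's decision. The one example given concerns shipment data in place of request data, not missing outcomes.

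**The concern.** Last observation carried forward (LOCF) assumes that a person who stops responding stays at the last recorded score. At the immediate follow-up the only earlier assessment named is baseline, so every missing score is set to no change, in both arms. The estimate then depends on how many people are missing from each arm as well as on what the intervention did.

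At 3 and 6 months the problem takes another form. People lost after the immediate follow-up carry forward a contrast from before all participants had the test and kit option. The second paper asks whether the effect lasts, and LOCF can create persistence if the effect fades or hide it if the effect remains.

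**Working it through.** The SAP states no attrition, SD, effect size or sample size, so there is no figure of its own to reproduce. The algebra follows from the rule. The numbers rest on assumptions, as marked.

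**1. Immediate follow-up, algebra.** Let Δ be the true effect, g the change common to both arms, and d_E and d_C the missing fractions in the experimental and control arms. Baselines are balanced and missingness is unrelated to outcome within arm. Mean change under LOCF is (1−d_E)(g+Δ) in the experimental arm and (1−d_C)g in control. The expected estimate is

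Δ(1−d_E) + g(d_C−d_E).

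- Equal missingness d: the estimate is Δ(1−d). There is no bias if Δ = 0.
- Unequal missingness, Δ = 0.5, g = 0.5:
  - 10% missing in the experimental arm v 30% in control: 0.5×0.9 + 0.5×0.2 = 0.55, overstated.
  - 30% v 10%: 0.5×0.7 − 0.5×0.2 = 0.25, understated.
- No effect, g = 1, missing 15% v 30%: 1×0.15 = 0.15 against the arm with more dropout.

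**2. Immediate follow-up, simulation.** Assumptions: 10 cohorts of 10 per arm, SD 1.3, ICC 0.03, within-person correlation 0.5, and a t-test on cohort means with 18 df (2,000 runs per scenario). With Δ = 0.6 and g = 0:

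| Missing, each arm | LOCF estimate | 95% CI coverage, unadjusted | Coverage, baseline-adjusted |
|---|---|---|---|
| 5% | 0.57 | 95% | 95% |
| 10% | 0.54 | 94% | 93% |
| 20% | 0.48 | 92% | 88% |
| 30% | 0.42 | 88% | 77% |

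Analysing the observed data instead gives about 95% coverage. Repeat simulations agreed to within about two percentage points. LOCF's model-based and empirical standard errors match (0.206 v 0.204 at 20% missing), so the undercoverage comes from bias. Baseline adjustment, which (c) allows, leaves that bias in place and narrows the interval around it.

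- Power at 20% missing, LOCF v observed data: 58% v 70% unadjusted; 85% v 87% adjusted; 79% v 88% adjusted if both arms rise 1 point.
- False-positive rate, Δ = 0, equal 25% missing: about 5%.
- False-positive rate, Δ = 0, g = 1: 10–15% at 15% v 30% missing; 7–9% at 10% v 20%.

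**3. Three months, algebra.** Let m1 be the share last seen at baseline and m2 the share last seen at the immediate follow-up, equal in both arms. LOCF estimates (1−m1−m2)Δ3 + m2Δ1, so the bias is

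m2Δ1 − (m1+m2)Δ3.

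It overstates if Δ3/Δ1 is below m2/(m1+m2) and understates if above. With Δ1 = 1.0, m1 = 10%, m2 = 20%:

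- effect gone: 0.20 − 0 = +0.20 (simulated false-positive rate 15%)
- half remains: 0.20 − 0.30×0.5 = +0.05
- two-thirds remains: 0.20 − 0.20 = 0
- all remains: 0.20 − 0.30 = −0.10

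If all losses precede the immediate follow-up (m1 = 30%, m2 = 0), there is no false effect, but the bias is −0.30 if the effect lasts in full. In the worst case (effect gone, m1 = 0), the false difference is 0.10 / 0.20 / 0.30 / 0.40 at 10 / 20 / 30 / 40% missing, with false-positive rates of 8 / 15 / 26 / 44%.

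**4. Six months.** With m3 the share last seen at 3 months, the bias is m2Δ1 + m3Δ3 − (m1+m2+m3)Δ6. If 20% carry the immediate score forward, an effect falling from 1.0 to 0.2 is estimated as 0.8×0.2 + 0.2×1.0 = 0.36. One rising from 0.2 to 1.0 is estimated as 0.8×1.0 + 0.2×0.2 = 0.84.

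**5. One item where carrying forward is partly right.** For naloxone requests, "the requests made at the immediate follow-up are counted for the 3-month follow-up". A carried 1 is therefore correct at 3 months; a carried 0 ignores any later request.

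**6. The alternative.** Maximum likelihood with baseline as a repeated outcome had bias of at most about 0.01 and coverage of 94–97% in all 14 three-month scenarios run (1,000 runs each). Missingness was completely at random within arm throughout.

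**The case against.** The strongest case for the plan has four parts.

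- **The sizes depend on chosen inputs.** This stands. With Δ1 = 0.6 instead of 1.0, the worst-case 3-month false-positive rates fall to about 6 / 8 / 13 / 20%. With g = 0.5 instead of 1, the 15% v 30% example gives 6–8%. A common rise of a full point is a strong assumption at a visit where controls do not yet have the kit option. The simulations also used cohort means, not the planned multi-level model.
- **The alternative was tested only where it should do well.** This also stands. People lost before follow-up may have attended little and gained little. If they gained nothing and g = 0, an observed-data effect of 0.60 with 20% missing corresponds to a true ITT effect of 0.6×0.8 = 0.48. LOCF would be right and maximum likelihood would overstate. This is a reason for a pre-specified missing-not-at-random analysis. It does not support LOCF as the primary rule, because LOCF fixes one untested assumption for both arms and, after the immediate visit, carries an early contrast forward.
- **Analyses (a) and (b) may reduce carried values** if attendance predicts follow-up. They may, but they also select on attendance, so a changed result could not be attributed to missing data. The permission to add analyses later pre-specifies nothing.
- **Under equal missingness the false-positive rate at the immediate visit stays near 5%**, and adjusted power at 20% missing hardly differs in the g = 0 case. Both are correct. The estimate is still too small and its interval covers too rarely.

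**Conclusion.** The concern holds. LOCF is the only missing-data rule stated for the primary analysis, and no pre-specified analysis replaces it. When missingness is unrelated to outcome, the immediate effect is understated by the missing fraction if dropout is equal. It can err in either direction, even under no effect, if dropout is unequal and both arms change. At 3 and 6 months the error depends on when people leave and how the effect evolves.

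The direction of each bias follows from algebra; its size cannot be fixed from the SAP. Under the assumptions shown, harm is trivial at 5% missing and clear from 20%. Dropout by arm and its timing cannot be known when the plan is set, so the rule should be changed and not left to turn out harmless.

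**What to change.** Replace LOCF as the primary method with the planned multi-level model fitted by maximum likelihood to all observed outcomes. Make baseline one of the repeated outcomes, so that participants with baseline only stay in the ITT set, and keep drug-use status as a covariate. A sound alternative is multiple imputation by arm that respects cohort and includes baseline and all earlier visits.

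Also:

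- pre-specify a delta-adjusted (missing-not-at-random) analysis;
- report missingness by arm and by last visit attended;
- keep LOCF, if at all, as a labelled sensitivity analysis.

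The cost is SAP wording and a little more analysis, with no new data. The standard error will be somewhat larger, about 0.18 v 0.15 (baseline-adjusted, 20% missing, under the assumptions above).

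### The SAP does not say whether a naloxone request made at the immediate follow-up still counts at 3 months when that assessment is missed; ordinary carry-forward scores it as a no

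*SAP*

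**What the plan says.** The primary outcome paragraph of the SAP defines item (d) as "requesting Naloxone before the assessment time point" and spells out the consequence: "the requests made at the immediate follow-up are counted for the 3-month follow-up". A first request at the immediate follow-up visit therefore scores 0 at that visit and 1 at 3 months. Item (d) is one of six yes/no items, and "The primary outcome is treated as a continuous variable, ranging from 0 to 6", so it is worth one point. Table 1 also lists requesting naloxone as a secondary outcome in its own right.

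The opening paragraph keeps everyone with a baseline measure in the primary analysis by "replacing missing data by carrying forward the last observation". It does not say whether this is done item by item or on the summed score.

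On access to kits, the SAP says of the test of the whole programme, kit availability included, that "that test is possible only for the immediate follow-up". It describes 3 and 6 months as the period "when all participants have the option of receiving HIV/HCV testing and Narcan kits".

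**The concern.** For a participant who first requests naloxone at the immediate follow-up and is then lost, the two rules give different answers at 3 months. The scoring rule gives 1. Carry-forward takes the last score, in which that request was deliberately left out, and gives 0.

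This differs from the general weakness of carry-forward, which substitutes a guess for an unknown value. Here the 3-month value follows from an event seen at an attended visit. Any imputation method that treated item (d) as missing would have the same fault.

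At stake are the 3- and 6-month contrasts on the composite and on the secondary outcome of requesting naloxone. If first requests at that visit are more common in one arm, the scoring alone shifts the comparison. As the SAP stands, two analysts could also score the same participant differently.

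**Working it through.** The SAP states no sample size, dropout rate or request rate, so there is no figure of its own to reproduce. The check is a scoring trace followed by an illustrative range.

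**Step 1: trace item (d) for a participant lost after the immediate follow-up.** The rule is 1 if the first request came before the time point, otherwise 0. The 6-month column assumes that earlier requests keep counting, which the SAP does not state.

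| First request | Scoring rule: immediate, 3, 6 months | Carry-forward: immediate, 3, 6 months |
|---|---|---|
| Before the immediate follow-up | 1, 1, 1 | 1, 1, 1 |
| At the immediate follow-up | 0, 1, 1 | 0, 0, 0 |
| Never | 0, 0, 0 | 0, 0, 0 |

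Only the middle row differs. The immediate follow-up value is the same under both rules in every row.

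**Step 2: does the level of carry-forward matter?** Carrying the composite forward includes the 0 for item (d). Carrying item (d) forward by itself also carries the 0. The error goes away only if the 3-month item is first derived from the recorded request and so is not treated as missing.

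**Step 3: bias in the arm difference.** Let r be the share of an arm first requesting at the immediate follow-up, and d the share of those people lost before 3 months. Each arm's 3-month mean on item (d) is too low by d × r. The bias in experimental minus control is

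dC × rC − dE × rE.

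**Step 4: illustrative values.** All rates are assumptions. Dropout d is set equal in the two arms.

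| d | rC | Bias, rE = 0 | Bias, rE = 10% |
|---|---|---|---|
| 10% | 20% | 0.1 × 0.2 = 0.02 | 0.1 × (0.2 − 0.1) = 0.01 |
| 20% | 40% | 0.2 × 0.4 = 0.08 | 0.2 × (0.4 − 0.1) = 0.06 |
| 30% | 60% | 0.3 × 0.6 = 0.18 | 0.3 × (0.6 − 0.1) = 0.15 |

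These are points on the 0–6 composite. Multiplied by 100, they are percentage points on the binary secondary outcome. A positive sign favours the experimental arm.

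**Step 5: when it vanishes or reverses.** With equal dropout and rE = rC the bias is 0. With dC = 10%, rC = 30%, dE = 40% and rE = 10%, it is 0.10 × 0.30 − 0.40 × 0.10 = −0.01, which favours control.

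**The case against.** The strongest reply is that the rules need not collide. Carry-forward applies to missing data, and a recorded request already fixes item (d) at 3 months, so there is nothing to replace. That reading is available, and an analyst who adopts it makes no error. But the SAP does not state it, and routine carry-forward does not produce it. This part of the reply turns a definite error into an unset precedence whose default gives the wrong value.

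A reader might also infer that the harm falls mainly on controls, so that the later results are tilted towards the experimental arm. The SAP does not establish this. It implies that controls gain the kit option around or after the immediate follow-up, but gives no date. If access comes after that visit, few control first requests fall on it and the effect is small. Experimental participants who first request at that visit are affected in the same way, and no request or dropout rates are given for either arm. This objection stands.

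The size also rests wholly on assumed rates. The 0.18 end combines the highest dropout, the highest rC and rE = 0. The relevant loss is that among people who requested at that visit, which may differ from overall dropout.

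The sensitivity analyses do not close the gap. None of those listed changes the carry-forward rule. The one that touches requests, "replacing the request data with the delivery/shipment data in the composite score", is only an example of what could be added, and it does not address loss to follow-up.

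**Conclusion.** The point holds as a gap between two stated rules. Under ordinary carry-forward, an observed request made at the immediate follow-up is scored 0 at 3 months for anyone then lost, and again at 6 months if requests accumulate and that assessment is missed too.

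The direction is conditional. If controls gain access around that visit and dropout is similar in both arms, the bias favours the experimental arm, by 0.02–0.18 composite points or 2–18 percentage points over the assumed range with rE = 0. It is zero if dC × rC = dE × rE, and it can change sign.

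The reach is limited to the 3- and 6-month results planned for the second paper. The immediate follow-up test of the whole programme does not change. The correction is worth making because misclassifying a known value is avoidable whatever its direction.

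**What to change.** Add to the primary outcome paragraph of the SAP:

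- A request recorded at or before the immediate follow-up sets item (d), and the secondary outcome of requesting naloxone, to 1 at 3 months even if that assessment is missed.
- Carry-forward is applied by item, and only to items whose value is not already known. The composite is then summed.
- Whether earlier requests keep counting at 6 months.

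The cost is a sentence or two and a small change to the derivation code. It uses request data collected at an attended visit, so no new data collection is needed. Later requests by people who miss assessments should be added only if the study holds dated request records; the SAP does not mention any.

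### Substance use frequency is analysed as a change score with no adjustment for its own baseline, which is less precise than baseline adjustment, and Table 1 leaves the role of baseline open

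*SAP*

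**What the plan says.** The SAP's paragraph on secondary and tertiary outcomes gives two rules. For binary outcomes, "we will specify a binomial family for the analysis of binary data". For change outcomes, "baseline responses will be subtracted from those obtained at the follow-up assessments", a step that the SAP denotes as T1 minus T0. Substance use frequency is the only outcome named under the second rule, and it is given as an example.

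Table 1 lists two related items in its tertiary column: "Substance use without a prescription or more than prescribed (with baseline level at 3 and 6 months" and "Injection substance use (with baseline level at 3 and 6 months". Neither entry states the scale of the item (yes/no, count or frequency) or how the baseline level enters the analysis.

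The opening paragraph describes the models for primary, secondary and tertiary outcomes "with the covariate of individuals' drug use status (i.e., PWUD versus PWNUD". No outcome's own baseline value is listed there. Baseline values appear as covariates only in the paragraph on sensitivity analyses, under item (c): "analyses including relevant baseline measures, GROV activities, intervention process evaluation, fidelity assessment".

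**The concern.** Read together, these places make the main analysis of substance use frequency a follow-up-minus-baseline difference, modelled on arm and drug use status. Subtraction fixes the weight on baseline at exactly one. When baseline and follow-up are imperfectly correlated, that weight is too large. Participants who start high tend to fall and those who start low tend to rise, so the difference keeps noise from the baseline measurement. Estimating the weight by using baseline as a covariate removes that noise.

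At stake are the width of the interval for the substance-use results and their exposure to whatever baseline difference the randomisation of cohorts happens to produce. Table 1 adds a second problem. Its wording can be read as subtraction or as adjustment, so an analyst could choose between two analyses of the same data after seeing them. If an item is yes/no, the subtraction rule also yields a variable that the binomial rule in the same paragraph cannot take.

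**Working it through.** The SAP gives no standard deviation, correlation or sample size for these outcomes, so there is no planned figure to reproduce. The comparison below is general.

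**Inputs**
- Outcome as follow-up minus baseline: SAP, paragraph on secondary and tertiary outcomes.
- Main-model covariate, drug use status only: SAP, opening paragraph.
- Correlation r between baseline and follow-up: not in the SAP. Assumed, range 0.3 to 0.7.
- Equal variance at baseline and follow-up, individual-level data, no clustering, no other covariate: assumed.

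**Step 1. Variance of the treatment estimate, relative to follow-up alone (= 1)**
- Change score: 1 + 1 − 2r = 2(1 − r)
- Follow-up adjusted for baseline: 1 − r²
- Ratio, change to adjusted: 2(1 − r) / [(1 − r)(1 + r)] = 2/(1 + r)

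| r | Change score | Baseline-adjusted | Variance ratio | Standard error ratio |
|---|---|---|---|---|
| 0.3 | 1.40 | 0.91 | 1.54 | 1.24 |
| 0.5 | 1.00 | 0.75 | 1.33 | 1.15 |
| 0.7 | 0.60 | 0.51 | 1.18 | 1.08 |

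The ratio exceeds 1 for every r below 1, so under these assumptions the direction does not depend on the value chosen for r. A simulation with 4,000 runs of 200 participants, individual level and without clustering, gave ratios of 1.53, 1.34 and 1.17.

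**Step 2. Chance baseline imbalance**

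Let D be the difference between arms in mean baseline use and τ the true effect. With equal variances, the expected follow-up difference given D is τ + rD. The expected change-score difference is therefore τ + rD − D = τ − (1 − r)D. At r = 0.3, 0.5 and 0.7, the estimate is shifted by 0.7D, 0.5D and 0.3D in the direction opposite to the imbalance. The baseline-adjusted estimate is centred on τ whatever D is. Over repeated randomisations D averages zero, so neither estimator is biased.

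**Step 3. A change score adjusted for baseline**

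Write Y for follow-up, B for baseline and G for arm. If Y − B = a + τG + βB, then Y = a + τG + (β + 1)B. The coefficient of G is the same in both. The simulation agreed to within 1e-14. The loss therefore comes from leaving baseline out of the model, not from subtraction as such.

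**Step 4. Yes/no items**

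A 0/1 follow-up status minus a 0/1 baseline status is −1, 0 or +1. A binomial family for binary data needs 0 or 1. This matters only if an item treated as a change outcome is recorded yes/no.

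**The case against.** The strongest reply is that a change score in a randomised comparison is a legitimate analysis. It is unbiased, regression to the mean acts in both arms, and preferring baseline adjustment is a matter of efficiency. That is correct, and the point is made on efficiency and chance imbalance only.

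Second, the main models already include drug use status, a marker of baseline use. It deals with imbalance between the two drug-use groups and may reduce the loss. It lowers the variance of a change score only so far as mean change differs between those groups, and it cannot tell heavy from light users among people who use drugs. It is a partial remedy of unknown size.

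Third, sensitivity analysis (c) adds relevant baseline measures. In a linear model that includes the item's own baseline value, Step 3 shows that this gives the baseline-adjusted estimate. It would reveal whether the choice matters, but it does not change the main result.

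Fourth, r is not documented, and the ratios ignore clustering. This limits the stated size.

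Some stronger readings are tempting but not supported:
- A reader might infer that text and Table 1 contradict each other. The table's reference to baseline may be shorthand for the same subtraction.
- A reader might infer that injection use is defined as a change score. The text names only substance use frequency, and injection use merely carries the same parenthesis in the table.
- A reader might infer that a differenced yes/no item will be put into a binomial model. The SAP does not state either item's scale, and its example of a change outcome is a frequency.
- A reader might infer that subtracting is worse than ignoring baseline. That holds only for r below 0.5. At r = 0.7 subtraction beats follow-up alone (0.60 against 1).
- A reader might infer a large imbalance from a small number of cohorts. The SAP does not give that number.

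**Conclusion.** The point holds as an available improvement and a wording ambiguity, not as an error that biases the trial. As written, the main analysis of substance use frequency omits its own baseline as a covariate. Under the assumptions listed, this costs between 18% (r = 0.7) and 54% (r = 0.3) in variance, or 8% to 24% in standard error. The actual figure could differ, because the models are multilevel, include drug use status, and rest on a correlation that the SAP does not report.

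For injection use the point is conditional on its being treated as a change outcome, and the binomial misfit is conditional on a yes/no scale. Both items are tertiary, so the primary outcome and its conclusion are untouched.

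**What to change.** 1. In the main analysis of substance use frequency, take the level at 3 months and at 6 months as the outcome and add that item's baseline value as a covariate beside drug use status. In a linear model, keeping the change score and adding the baseline value gives the same treatment estimate, so the sponsor can keep its change measure.
2. Do the same for injection use if it is treated as a change outcome.
3. For any item recorded yes/no, use a binomial model on follow-up status with baseline status as a covariate, and do not subtract.
4. State the scale of each item and what T0 and T1 denote. Name the single model that goes with each scale, and use the same wording in the text and Table 1.

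The cost is a sentence or two in the SAP and a matching edit to two table entries. No new data are needed, because the subtraction already requires the baseline responses. If the sponsor reports levels instead of change, the results text must describe the effect as a difference at follow-up given baseline.
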